The Phase II portion is a randomized two-arm study to evaluate immune response, efficacy and safety of the combination of nivolumab and CCR2/CCR5 dual-antagonist (BMS-813160) with and without GVAX. We will be monitoring the toxicities for each arm in the Phase II portion, and if we observe >33% unacceptable toxicities in the first 6 patients or any time afterwards in any arm, we will halt the enrollment pending safety evaluations.

DLTs will be assessed in the first cycle of Phase I, starting Cycle 1 Day 1 through prior to initiation of Cycle 2. Unacceptable toxicities will be used to monitor safety from Cycle 2 Day 1 of Phase I through to end of study treatment and from Cycle 1 Day 1 of Phase II through to end of treatment. During periods of standard of care treatment (FOLFIRINOX-based chemotherapy, SBRT, Surgery) only AEs considered related to study treatment will be collected. If patients develop adverse events (AEs) to any of the three immunotherapies

A Phase I/II trial of combination immunotherapy with nivolumab and a CCR2/CCR5 dual antagonist (BMS-813160) with or without GVAX following chemotherapy and radiotherapy for locally advanced pancreatic ductal adenocarcinomas (PDACs)

(BMS-813160, nivolumab or GVAX) leading to its/their discontinuation, they will be taken off the trial.

All patients will undergo standard of care evaluations consisting of history and physical, CT of the chest/abdomen/pelvis or MRI abd/pelvis and non-contrast CT chest (if do not tolerate contrast) to evaluate for local progression and metastatic disease while they are on study.

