12.2 Sample Size/Accrual Rate

Each year, approximately 250 patients with newly diagnosed locally advanced pancreatic cancer are seen at JHH. Approximately, 50% of these patients will potentially be enrolled in clinical trials.

Phase I: 3-12 patients (3+3 design with Nivo+GVAX+BMS-813160 at two dose levels, primary endpoint - safety).

Phase II: up to 15 patients (primary endpoint - immunologic)

The first 10 patients will be randomized 1:1 into two arms:

Arm A: *nivolumab*+ *BMS-813160*

Arm B: *nivolumab*+ *BMS-813160*+ *GVAX*

Up to 5 additional patients will be assigned to Arm C: *nivolumab* + *BMS-813160* in Cycle 1

Due to the availability of BMS-813160, the enrollment of Phase II Arm A and Arm B will close early before full accrual under the original protocol. An amendment is required to change the design of the phase II portion. The analysis plan is also changed accordingly. The primary endpoint remains to be immunologic response, defined in Section 12.1 above.

The analysis will be performed separately in two groups of patients receiving either *nivolumab*+ *BMS-813160* (Group 1), or *nivolumab*+ *BMS-813160*+ *GVAX* (Group 2). Group 2 will include patients treated with the triplet regimen at the RP2D during both Phase II and Phase I portion. We expect up to 10 patients in Group 2 (including 6 treated at the 300mg dose in Phase I and 5 patients in Arm B of Phase II). A rate of immune response of 5% or lower is not considered worthy of further investigation, whereas immune response rate of at least 30% is consider worthy of further study.

Group 1 will have 8, up to 10, patients treated with the doublet regimen during Phase II (including up to 5 patients in Arm A and 3 to 5 patients anticipated to be enrolled to Arm C who receive *nivolumab* + *BMS-813160* in Cycle 1 and *nivolumab* + *GVAX* from Cycle 2 and after). It allows us to make preliminary assessment of immune response.

The probability of events under different true immune response rate is as follow:

number of responders out of 8 patients	True response rate				
	0.3	0.25	0.2	0.1	0.05
>=1	0.943	0.900	0.832	0.570	0.337
>=2	0.745	0.633	0.497	0.187	0.057
>=3	0.448	0.321	0.203	0.038	0.006
number of responders out of 10 patients					
	0.3	0.25	0.2	0.1	0.05
>=1	0.972	0.944	0.893	0.651	0.401
>=2	0.851	0.756	0.624	0.264	0.086
>=3	0.617	0.474	0.322	0.070	0.012

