12.5 Analysis of Secondary Endpoints – Phase II Safety Assessment

The safety analysis will be performed in all treated subjects. AE data will be listed individually and incidence of AEs summarized by system organ class and preferred terms within a system organ class for each treatment group. When calculating the incidence of AEs, each AE (based on preferred terminology defined by CTCAE version 5.0) will be counted only once for a given subject. In analyses of grade and causality, if the same AE occurs on multiple occasions, the highest grade and strongest relationship to study drug will be assumed. If 2 or more AEs are reported as a unit, the individual terms will be reported as separate experiences.

Changes in vital signs, hematology and clinical chemistry parameters from baseline to the end of the study will be examined. Toxicity will be tabulated by type and grade. Toxicities will be characterized according to the CTCAE version 5.0. Treatment-emergent changes from normal to abnormal values in key laboratory parameters will be identified.

We will monitor adverse events in phase II, and if we observe >33% unacceptable toxicities in the first 6 patients or any time afterwards in any arm, we will halt the enrollment pending safety evaluations. Specifically, we stop if:

Number of patients in the same arm with AE \geq	2	3
In number of patients in that arm between	2-6	7 - 9

The operating characteristics of the stopping rule for toxicity are shown below and are based on 5000 simulations:

Risk of AE	0.10	0.20	0.25	0.30	0.33	0.40	0.45
% of Time study stops	12.2%	37.8%	52.8%	65.3%	71.6%	83.7%	89.8%
Expected sample size	8.66	7.98	7.57	7.21	7.03	6.66	6.45

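### The Phase II toxicity boundary and its operating characteristics in section 12.5 describe a 9-patient arm first examined at patient 6, while the amended arms have 5, 5 and 3 to 5 patients

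*Combined protocol and SAP*

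**What the plan says.** Section 12.5 puts the rule in words, with entry suspended until safety has been assessed: "if we observe >33% unacceptable toxicities in the first 6 patients or any time afterwards in any arm, we will halt the enrollment pending safety". Section 1.7 has the same trigger: "if we observe >33% unacceptable toxicities in the first 6 patients or any time afterwards in any arm". Section 12.5 then makes it specific in a two-column boundary. The row "Number of patients in the same arm with AE" holds 2 and 3 as minimum counts, and the row "In number of patients in that arm between" holds 2-6 and 7-9. Below it come results for risks from 0.10 to 0.45, introduced by this sentence: "The operating characteristics of the stopping rule for toxicity are shown below and are based on 5000 simulations". At a 33% risk the study stops 71.6% of the time, with an expected sample size of 7.03.

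Section 4.8, the protocol's own stopping-rules section, uses the same 33% trigger per arm but gives no minimum number of patients.

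Section 12.2 sets the amended size: "The first 10 patients will be randomized 1:1 into two arms", and "Up to 5 additional patients will be assigned to Arm C", with 3 to 5 anticipated there. It lists up to 5 patients in Arm A and 5 in Arm B, and says that the analysis plan was changed to match the new design.

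**The concern.** The toxicity rule is counted within an arm, yet no planned arm reaches the sixth patient named in the narrative, still less patients 7 to 9. The table appears to have been carried over from a larger design. A sponsor, ethics board or monitoring board reading section 12.5 would take it that an arm with a 33% rate of unacceptable toxicity has about a 72% chance of being halted. That figure belongs to a design no longer in use. There is also a conflict within section 12.5: the boundary starts at patient 2, while the expected sample sizes never fall below 6.

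**Working it through.** **Inputs.** The boundary, the risks and the printed results come from section 12.5, and the arm sizes from section 12.2. Assumptions: outcomes are independent with constant risk p, and each is known before the next patient enters.

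**1. Reproducing the printed table.** Take at most 9 patients, a first look at patient 6 (stop at 2 or more), then looks at 7, 8 and 9 (stop at 3 or more). At p = 0.33:

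- P(2 or more in 6) = 1 − 0.67^6 − 6(0.33)(0.67^5) = 1 − 0.0905 − 0.2673 = 0.6422.
- One event in 6, then at least 2 in the next 3: 0.2673 × 0.2548 = 0.0681.
- No event in 6, then 3 in 3: 0.0905 × 0.0359 = 0.0033.
- P(stop) = 0.6422 + 0.0681 + 0.0033 = 0.714.
- A stop at patient 8 needs one event in 6, then two in a row: 0.2673 × 0.1089 = 0.0291. No stop is possible at 7.
- E[N] = 6(0.6422) + 8(0.0291) + 9(0.3287) = 7.04.

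The exact recursion over all risks gives:

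| Risk | 0.10 | 0.20 | 0.25 | 0.30 | 0.33 | 0.40 | 0.45 |
|---|---|---|---|---|---|---|---|
| Stop %, printed | 12.2 | 37.8 | 52.8 | 65.3 | 71.6 | 83.7 | 89.8 |
| Stop %, exact | 12.5 | 38.8 | 52.4 | 64.8 | 71.4 | 83.5 | 89.7 |
| E[N], printed | 8.66 | 7.98 | 7.57 | 7.21 | 7.03 | 6.66 | 6.45 |
| E[N], exact | 8.65 | 7.95 | 7.58 | 7.23 | 7.04 | 6.67 | 6.46 |

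Agreement is within 1.0 point and 0.03 patients, which is compatible with 5000 simulations (standard error √(0.714 × 0.286/5000) = 0.6 points at a 33% risk). A maximum of 8 gives 67.1% at a 33% risk, and a maximum of 10 gives E[N] = 7.33, so neither fits. Looks at 6 and 9 only give 7.07, a slightly worse fit that still has 9 patients and a first look at 6.

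**2. The boundary as printed, with 9 patients.** Acting from patient 2 leaves the stop percentages unchanged but lowers E[N]. Summing P(N > n) for n = 0 to 8 at p = 0.33: 1 + 1 + 0.891 + 0.745 + 0.599 + 0.468 + 0.358 + 0.358 + 0.329 = 5.75, against the printed 7.03. At p = 0.45 it is 4.48 against 6.45. The sample-size row therefore does not belong to the boundary above it, whatever the arm size.

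**3. The boundary as printed, with the planned arms.** In an arm of n ≤ 6, P(cross) = 1 − (1 − p)^n − np(1 − p)^(n−1). At p = 0.33, n = 5: 1 − 0.1350 − 0.3325 = 0.532.

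| Risk | 0.10 | 0.20 | 0.25 | 0.30 | 0.33 | 0.40 | 0.45 |
|---|---|---|---|---|---|---|---|
| Printed % | 12.2 | 37.8 | 52.8 | 65.3 | 71.6 | 83.7 | 89.8 |
| n = 5, % | 8.1 | 26.3 | 36.7 | 47.2 | 53.2 | 66.3 | 74.4 |
| n = 4, % | 5.2 | 18.1 | 26.2 | 34.8 | 40.1 | 52.5 | 60.9 |
| n = 3, % | 2.8 | 10.4 | 15.6 | 21.6 | 25.5 | 35.2 | 42.5 |

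For n = 5 the shortfall runs from 12.2 − 8.1 = 4.1 to 71.6 − 53.2 = 18.4 points. For n = 3 it runs from 12.2 − 2.8 = 9.4 to 83.7 − 35.2 = 48.5 points.

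**4. The other two readings.** If no look is made before patient 6, an arm of 5 or fewer crosses with probability 0. Under section 4.8 read literally, a single event among the first three patients is enough (1/3 = 33.3%, and section 12.5 itself treats 2 of 6 as crossing). Two events in patients 4 and 5 after none in the first three also suffice (2/5 = 40%). For n = 5 at p = 0.33 this gives (1 − 0.67^3) + 0.67^3 × 0.33^2 = 0.699 + 0.033 = 73.2%. At p = 0.10 it gives 0.271 + 0.007 = 27.8%, against the printed 12.2%.

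**5. Crossing while a patient is still to enter.** Under the printed boundary at p = 0.33, this is the chance of 2 or more events among the first n − 1 patients: 40.1% for n = 5, 25.5% for n = 4, and 0.33^2 = 10.9% for n = 3.

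**The case against.** A reader might infer that the current arms have no toxicity protection, because the rule can never fire before patient 6. The documents do not establish that. Section 12.5 presents the boundary as the specific form of the rule, and its first column begins at 2. The narrative phrase about the first 6 patients can also mean at any time during them. Only the simulated expected sample sizes clearly imply a look at 6. The 0% result is one contestable reading.

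Nor were the stop percentages miscalculated. They are right for a 9-patient arm; the fault is that they were carried over.

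The practical stakes are also modest. Enrollment closed on December 19, 2022 (sections 1.7 and 4.1), and Arm C takes only patients already enrolled but not yet randomized. A halt has little or nothing left to act on in Arms A and B. Weekly safety meetings (11.2), monitoring-board review at least annually (11.3) and individual discontinuation (4.9) continue regardless, and no primary analysis uses the rule. All of this stands and lowers the priority.

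Two other defences fail. The pooled Groups 1 and 2 of section 12.2 are larger, but they serve the immune-response analysis, while the toxicity rule counts patients in the same arm. Unequal arms are conceivable, since blocking is not stated, but even an arm of 6 would cross with probability 64.2% at a 33% risk, still below 71.6%.

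**Conclusion.** The point holds as an inconsistency left by the amendment. The printed operating characteristics apply to no planned arm, and the sample-size row disagrees with the printed boundary independently of arm size. Under that boundary protection is reduced, not absent: 53.2%, 40.1% or 25.5% at a 33% risk for 5, 4 or 3 patients, instead of 71.6%. The result would be 0% only if no look precedes patient 6. Under section 4.8 taken literally the chance of halting would not be lower at all, but halts at a low risk would be more frequent than printed. The operating characteristics are therefore undetermined until the sections agree. These figures assume the planned 5/5 split and immediately known outcomes. Because toxicities are followed to the end of treatment, crossings recognized in time to stop entry would be rarer than the figures suggest.

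**What to change.** Reconcile sections 1.7, 4.8 and 12.5 on when looks start and what triggers a halt; that choice is the sponsor's. Remove the 7-9 column, which no planned arm can reach. Replace the simulated table with exact values for arms of 3, 4 and 5 under the reconciled rule, including expected sample sizes that fit those arms. If the boundary of 2 or more from patient 2 is kept, the stop probabilities are those in step 3. For an arm of 5, E[N] is then 4.91, 4.68, 4.52, 4.35, 4.23, 3.96 and 3.76 across the seven risks. Add a note that crossing on an arm's last patient leaves no enrollment to halt.

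The cost is one table and a few sentences, with no change to sample size or to the primary analysis. If that boundary is kept, the stated probabilities fall by about 4 to 18 points for an arm of 5 and about 9 to 49 points for an Arm C of 3.

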12.6 Analysis of Secondary Endpoints – Efficacy Assessment

The secondary endpoints of interest are OS, MFS and LPFS, which are defined as the time from the study treatment initiation until death, evidence of metastatic disease or local

A Phase I/II trial of combination immunotherapy with nivolumab and a CCR2/CCR5 dual antagonist (BMS-813160) with or without GVAX following chemotherapy and radiotherapy for locally advanced pancreatic ductal adenocarcinomas (PDACs)

progression, respectively. The evaluable populations for OS, MFS and LPFS includes all subjects who receive at least one dose of study drugs (nivolumab, BMS-813160, or GVAX), and there will be a subgroup analysis for those who complete one cycle of study combination immunotherapy. If a patient is lost to follow-up, withdraws from the study or dies prior to being diagnosed with metastatic disease or local progression, or the study is ended prior to death, the patient will be considered censored at their last recorded follow-up. Kaplan-Meier survival curves will be constructed and the median survival estimates will be calculated with 95% confidence intervals using Greenwood's formula. Survival curves will be compared to historical data using log rank test. Because the study sample size is not powered for comparing the OS and MFS, comparisons with historical data will be performed for explorative purpose. Proportions of surgical resectability and pathologic response will be reported along with the corresponding binomial exact 95% confidence intervals.

Other secondary endpoints include surgical resectability and pathologic response. Surgical resectability will be determined by review of imaging and review of the subject's surgical candidacy (clinical status and tumor status) off trial after the patient completes off-trial chemotherapy and radiotherapy. Pathologic response will be graded after surgical resection or biopsy with comparisons of pre-and post-immunotherapy core biopsies or surgical samples. For each outcome, the proportion will be calculated with an exact 95% confidence interval. Individuals who drop out of the study due to treatment toxicity or other causes prior to outcome assessment will be counted as not resectable and non-responders. Logistic regression will be used to assess the impact of risk factors on each outcome. Time to event analyses will be used to assess the timing of resection and response.

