1.5.1 Efficacy Endpoints

- OS from the time of Cycle 1, Day 1 of immunotherapy until death from any cause.
- MFS from the time of Cycle 1, Day 1 of immunotherapy until first documented distant metastases on imaging or death, whichever occurs first.
- LPFS from the time of Cycle 1, Day 1 of immunotherapy until first documented local progression on imaging or death, whichever occurs first.
- Surgical resectability determined by successful performance of resection (as defined by R0 and R1 resection).
- Pathologic response as determined by surgical margins and residual disease.

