After completion of SBRT, the patients will then be re-evaluated for eligibility for continuation in the study and must have LAPC based on NCCN Guidelines as determined by review of CT, PET, or MRI imaging at our institution. Patients who have developed metastatic disease are no longer eligible to continue in the study. If the patients remain eligible for continuation in the study after rescreening, they will be assigned or randomized to a study arm (depending on when they were enrolled).

Due to availability of BMS-813160, study enrollment was closed as of December 19, 2022. Patients randomized prior to this will continue receiving study treatment as planned until drug supply expires on July 31, 2023, then will continue to receive any remaining study cycles without BMS-813160. Any patients who were enrolled but not randomized prior to December 19, 2022 (i.e. those receiving chemotherapy) will be assigned to a new arm (Arm C).

In phase I, the combination immunotherapy consists of nivolumab, CCR2/CCR5 dual-antagonist (BMS-813160) and GVAX. In phase II, the first 10 patients will be randomized 1:1 between Arm A and Arm B. Remaining patients will be assigned to Arm C.

Arm A subjects receive nivolumab and BMS-813160, Arm B subjects receive nivolumab, BMS-813160, and GVAX, and Arm C patients will receive nivolumab and BMS-813160 for Cycle 1 (prior to surgery) and then nivolumab and GVAX for Cycles 2 and beyond.

After randomization or assignment to a study arm, subject will receive Cycle 1 of the combination immunotherapy. Cycle 1 lasts 28 days and will start within two weeks of completion of SBRT.

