9. STUDY SCHEDULE

Patients will be evaluated and consented at the time of initial diagnosis of LAPC. Patients should meet all eligibility criteria and complete all screening procedures prior to starting SOC chemotherapy, however they can be enrolled up to one month after initiating SOC chemotherapy to allow for time to gather all records from outside institutions if necessary. Patients will then receive 8-16 14-day cycles of FOLFIRINOX-based chemotherapy, followed by SBRT between 2-4 weeks after completion of chemotherapy. Both chemotherapy and radiation therapy are standard therapies for LAPC, and will be administered off-trial. They will have another evaluation for eligibility to receive immunotherapy after completion SBRT at which point they will be randomized during Phase II and they will initiate Cycle 1 Day 1 of combination immunotherapy within 2 weeks of completion of SBRT. The patient will undergo Post-Immunotherapy Evaluation within one week after Cycle 1 Day 28.

Pre-surgical Study Schedule						
Procedure	Screening/ Baseline	Pre-Immunotherapy Screening (within 3 weeks prior to C1D1)	Cycle 1 Immunotherapy (within 2 weeks after completion of SBRT)			End of Cycle 1 (day before surgery or C1D28, whichever is earlier) ²⁴
			C1D1 ²	C1D2 ³	C1D15 ⁴	
Visit Window ¹ (days)			-	-	+3	-3/+14
Nivolumab (All patients)			X			
GVAX (Phase 1 and Arm B patients)				X		
BMS-813160 (All patients) ⁵			X	X	X	X
Eligibility criteria	X	X				
Randomization (Phase 2 only) ⁶		X				
Demographics	X					
Medical History ⁷	X	X				
Medications	X	X	X		X	X
Physical Exam ⁸	X	X	X			X
Vital Signs and pulse ox ⁹		X	X	X	X	X
Height ⁹		X				
Weight		X	X		X	X
Performance Status	X	X	X		X	X
EKG for PR, QRS and QTcF ¹⁰		X	X		X	X
Hematology profile ^{11, 12}	X	X	X		X	X
Chemistry profile ^{11, 13}	X	X	X		X	X
TSH ^{11, 14}		X	X			X
Serum/Urine Preg ^{11, 15}	X	X	X			
CA 19-9 ¹¹	X	X	X			X
Urinalysis and microscopic exam ^{11, 16}		X				
INR ¹¹		X				
HLA-Typing ¹¹			X			
Adverse event evaluation		X	X		X	X
Vaccine Site Assessment						X
PET-CT, CT, or MRI ¹⁷	X	X				X ¹⁸
Tumor measurements ¹⁷	X	X				X ¹⁸
Pathology Review	X	X				
Peripheral blood for research (up to 100cc) ¹⁹			X			X
Serum (20cc) ¹⁹			X			X
Plasma (20cc) ¹⁹			X			X
Archival Tissue ²⁰	X					
EUS Core Biopsy ¹⁹		X ²¹				X ²²
QoL Questionnaire ²³			X			X

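### The one-cycle-completer subgroup for OS, MFS and LPFS keeps its clock at Cycle 1 Day 1, so its estimates include guaranteed time, most clearly for OS

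*Combined protocol and SAP*

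**What the plan says.** Section 12.6 takes all patients with at least one dose of any study drug as the population for OS, MFS and LPFS. It then states that "there will be a subgroup analysis for those who complete one cycle of study combination immunotherapy".

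The time origin is the same throughout. Section 12.6 has the endpoints "defined as the time from the study treatment initiation until death" or the relevant progression event. Section 1.5.1 is more specific and lists "OS from the time of Cycle 1, Day 1 of immunotherapy until death from any cause". Its entries for the other two endpoints share that starting point; one counts distant metastasis or death as the event, the other local progression or death.

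Sections 10.1.3 to 10.1.5 also start the clock at the beginning of treatment. No landmark, delayed entry or separate origin is given for the completers.

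On the length of the cycle, Section 1.7 says "Cycle 1 lasts 28 days and will start within two weeks of completion of SBRT". The pre-surgical schedule in Section 9 places the End of Cycle 1 visit at "day before surgery or C1D28, whichever is earlier", with a window of -3 to +14 days. Section 12.6 plans log-rank tests of the survival curves against historical data and calls those comparisons exploratory because the study is not powered for OS and MFS.

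**The concern.** Whether a patient belongs to this subgroup becomes known only about four weeks after the clock starts. A patient who dies during Cycle 1 cannot have completed it. Distant metastasis, unacceptable toxicity and discontinuation of any study drug also end treatment under Sections 1.7 and 4.9, so they too can prevent completion. The subgroup's early follow-up is therefore protected from some events by the way the patients were chosen, yet it is counted as survival time. The direction is known: the estimates are too favourable.

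Two features give this some weight. The secondary objectives in Section 1.2 set OS, MFS and LPFS against historical controls, and nothing says that those controls must have survived a matching interval. Completers of one cycle are also the evaluable population for the Phase II immune endpoint in Section 12.4, so their survival may well be reported beside the immune response. The second point is an inference, not a stated plan.

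**Working it through.** The documents give no event count, power or alpha for these endpoints, so there is no planned figure to reproduce. What can be checked is the size of the shift under a stated model.

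**Inputs**
- Guaranteed interval L: 28 days (Section 1.7) / 30.44 days per month = 0.92 month.
- Illustrative medians m from the historical SBRT study in Section 2.2: OS 13.9 months (95% CI 10.2 to 16.7) and MFS 7.7 months (5.8 to 10.2). Using them here is an assumption, because the study's time origin is not given.
- Model, assumed: constant hazard λ = ln 2 / m, and no treatment effect.

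**Formulas**
- Share with an event before L: 1 − exp(−λL).
- Among patients event-free at L but timed from Cycle 1 Day 1, S(t) = exp(−λ(t − L)). This reaches 0.5 at t = m + L, so the inflation is L/m.
- Timed from a landmark at L, the median returns to m.

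**Results for L = 0.92 month**

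| Endpoint | m (months) | Event before day 28 | Median read in completers | Inflation |
|---|---|---|---|---|
| OS | 13.9 | 4.5% | 14.82 | +6.6% |
| OS, lower limit | 10.2 | 6.1% | 11.12 | +9.0% |
| OS, upper limit | 16.7 | 3.7% | 17.62 | +5.5% |
| MFS (at most) | 7.7 | 7.9% | 8.62 | +11.9% |
| MFS, lower limit (at most) | 5.8 | 10.4% | 6.72 | +15.9% |
| MFS, upper limit (at most) | 10.2 | 6.1% | 11.12 | +9.0% |

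Twelve-month OS would read 57.5% instead of 55.0%. A simulation of 2,000,000 exponential OS times gave medians of 13.89 months for all patients, 14.81 for completers timed from Cycle 1 Day 1, and 13.89 for completers timed from day 28.

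**Length of the interval.** Section 12.6 does not define completing a cycle. At the short end, surgery five weeks (35 days) after SBRT, with Cycle 1 starting 14 days after SBRT, falls on day 21, so the day before is day 20. At the long end, the visit window allows 28 + 14 = 42 days. The shift then runs from 20/30.44 = 0.66 to 42/30.44 = 1.38 months. At m = 13.9 that is an OS median of 14.56 (+4.7%) to 15.28 (+9.9%).

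**Endpoint by endpoint**
- OS: the conditioning is complete, because a completer must have been alive.
- MFS: the table overstates the effect. Section 9 (footnotes 17 and 18) schedules imaging at pre-immunotherapy screening and at the post-immunotherapy surgical evaluation, with none planned in between. Metastases first seen on the later scan can remain in the subgroup. Only deaths and metastases found on unscheduled scans are selected out.
- LPFS: Section 1.7 lets patients with local progression stay on treatment, so only the death component is conditioned on. Section 12.6 also appears to censor deaths that precede progression, contrary to Sections 1.5.1 and 10.1.5. Under that reading almost no guaranteed LPFS time would remain.

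**Scale against noise.** Section 12.2 expects up to 10 patients per group. Expected deaths before day 28 are 10 × 0.045 = 0.45, and the chance of none is 0.955^10 = 0.63. The 49-patient study in Section 2.2 has an OS interval 16.7 − 10.2 = 6.5 months wide.

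**What a landmark leaves behind.** Suppose that 20% of patients are living non-completers with twice the hazard (both figures assumed). Median OS is then 12.00 months for all treated, 14.80 for completers from Cycle 1 Day 1, and 13.88 for completers from day 28. The landmark removes the 0.92 month of guaranteed time. The remaining gap of 13.88 − 12.00 = 1.88 months is selection.

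**The case against.** Section 12.6 already limits the harm. The main population is everyone dosed, the completers are called a subgroup, and the historical comparisons are called exploratory. It does not say expressly that the log-rank test applies to the subgroup, although it does not exempt it either. Patients are also re-screened after chemotherapy and SBRT for performance status, organ function and absence of metastasis (Sections 3.3 and 3.4). Their early hazard may therefore be below average and the shift smaller than a constant hazard gives. With no early death, the likelier outcome in a group of 10 under this model, no patient is removed from the OS subgroup by dying. All of this stands. It makes the point modest but does not supply the missing time origin.

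Three stronger readings are tempting and unsupported:

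- A reader might infer that all three endpoints are inflated alike. The rule on local progression and the scan schedule say otherwise.
- A reader might run the guaranteed interval to surgery, up to seven weeks or 49 days. Those weeks count from the end of SBRT, and Section 9 ends Cycle 1 at the earlier of the day before surgery and day 28. Even with the visit window the limit is 42 days.
- A reader might infer that the trial's survival results as a whole are biased. The all-treated analysis does not condition on completion.

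**Conclusion.** The point holds for the completer subgroup. As written, its estimates contain guaranteed time and are biased upward. For OS the expected shift is 0.92 month (+6.6% at a median of 13.9, and +5.5% to +9.0% over the cited confidence limits). For MFS, 0.92 month (+12% at a median of 7.7) is an upper bound. For LPFS only deaths contribute, and no separate figure can be given. These sizes rest on a constant hazard, a 28-day interval and medians borrowed from a different regimen. The shift is well below sampling error in about 10 patients per group and would not by itself change a conclusion. It is nevertheless systematic, runs in the favourable direction and can be removed without new data, so it is worth correcting in a secondary analysis.

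**What to change.** In Section 12.6:

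1. Define completion of one cycle so that it is known by a fixed day, for example day 28 after Cycle 1 Day 1. The End of Cycle 1 visit should not serve as time zero, because its date varies by patient.
2. Make the completer subgroup a landmark analysis from that day, including only completers who are alive and free of the endpoint event then.
3. Apply the same landmark to any historical comparator. If its event times are not available, report the subgroup descriptively without a log-rank test.
4. Keep the all-treated analysis from Cycle 1 Day 1 as the main one, and state that the landmark removes guaranteed time but not the selection of fitter patients.
5. Reconcile the handling of deaths for MFS and LPFS in Section 12.6 with Sections 1.5.1, 10.1.3 and 10.1.5, since it determines how much of the issue remains for LPFS.

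The cost is a short change to the text, with no new visits or data collection in this trial. The subgroup median will be slightly shorter and measured from the landmark, one or two patients may drop out of the subgroup, and the historical comparison will need individual event times.
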